6.3 Per Protocol Population

The Per Protocol (PP) population will include all subjects in Arms 1 and 2 who pass screening, undergo the assigned treatment, and have complete and evaluable Week 24 data, except that:

Subjects will be excluded from the Per Protocol Population if one or more of the following occurs:

- 1. Discontinuation from the study.
- 2. Incomplete or missing data for the endpoint.
- 3. [Arm 1 only] Change to RLS medication during the study that is deemed clinically significant by the investigator.
- 4. [Arm 1 only] Zero total device uses during the study.
- 5. Other protocol deviation occurs that is deemed clinically significant by the investigator.

The PP Population will be used for a secondary analysis of all efficacy endpoints.

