16.15. Study Exit

Study exit will occur at the conclusion of Eval #9. At study exit, the Investigator/coordinator will complete the study exit eCRF. Adverse events unresolved at study exit will be followed by the Investigator until resolution occurs or at least 30 days after the subject's participation in the study is complete.

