17.2.3. Efficacy Analysis

A Statistical Analysis Plan (SAP) will be developed prior to completion of the first subject in Arm 1 or 3, which will include a plan for efficacy analysis. The following analyses are planned:

- Primary statistical analysis may be conducted separately for subjects in Arms 1 and Arm 3.
 Additional pooled analysis across Arms 1 and 3 may also be conducted.
- Subgroup analysis form Arms 1 and 3 may be conducted based on the following criteria:
 - o Responders at Week-8 of The RESTFUL Study, as defined by CGI-I of 1 or 2.
 - o Non-responders at Week-8 of The RESTFUL Study, as defined by CGI-I of 3 or above.
- Missing data may be addressed with the use of multiple imputation.
- Appropriate statistical techniques will be employed to test statistical significance.
- If there is success on the primary endpoint, then secondary endpoints will be tested in order,
 according to the fixed-sequence method, until failure.

The analysis cohort for the primary efficacy endpoint are subjects who are enrolled and undergo the assigned treatment.

The Per Protocol analysis will exclude subjects for whom one or more of the following apply:

- 1. Dropout or removal from the study.
- 2. Incomplete or missing data for the endpoint.

Clinical Trial

Investigational Plan, Protocol CT-05 (Extension Study)

Document #: CT-4

Rev: 1.0

Effective: 11/24/2021

- 3. Clinically significant change in dose or schedule of medication that affects RLS symptoms.
- 4. New medical information available after randomization indicates an exclusion criterion.
- 5. Other protocol deviation occurs that is deemed clinically significant by the investigator.
- 6. Device usage at or after bedtime on fewer than two-thirds of the nights with RLS symptoms at or after bedtime, as reported by the subject on the Weekly Questionnaire assessments.
- 7. Missing two or more follow-ups (Follow-ups completed out-of-window are not considered "missing")
- 8. Zero total device uses.

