3.1 Overview

Subjects who previously completed the RESTFUL Study [Protocol Number: CT-04; ClinicalTrials.gov Identifier: NCT04874155] consent to one of two Arms, the design of which is

illustrated in the flowchart below (Figure 1). Arm 1 is a Direct Roll-Over Extension and Arm 2 is a Control.

- **Arm 1** (Direct Roll-Over Extension) Arm 1 is only an option for subjects who successfully complete RESTFUL Study after enrollment to CT-05 begins at a given clinical site; Arm 1 involves a 24-wk extension period of NTX100 device use followed by an 8-wk period without device use. Subjects in Arm 1 are instructed to maintain constant dose and schedule of RLS medication (if applicable).
- Arm 2 (Control Group) Arm 2 is an option for subjects who successfully complete the RESTFUL Study before enrollment to CT-05 begins at a given clinical site or subjects who decline to participate in Arm 1. Subjects enrolled in Arm 2 will receive no treatment with the NTX100 device during Arm 2. Arm 2 involves assessment during the 24-wks after RESTFUL Study completion. Subjects in Arm 2 are permitted to change RLS medication.

Figure 1: Study Design Flowchart

The schedule of assessments for this study is presented in Table 1.

Table 1: Schedule of Assessments

	Eval 1			Eval 2	Eval 3	Eval 4	Eval 5	Eval 6	Eval 7	Eval 8	Eval 9	
	Day 0	Wks 1-24	Wks 25-32	Wk-2	Wk-4	Wk-8	Wk-12	Wk-16	Wk-20	Wk-24	Wk-32	
	In-person	Remote	Remote	Remote	Remote	In-person or Remote**			Remote	In-person	Remote	
Completed by												
	X											
	X											
Staff + subject	X											
Subject		X										
Subject			х									
Staff				X	X	x	X	x	X	X		
Staff	X			Х	Х	x	X	Х	Х	х	X	
Staff				X	Х	x	X	x	X	Х	X	
Staff + subject				Х	Х	x	Х	Х	Х	х	X	
Staff + subject				X	X	x	X	x	X	X	X	
Investigator + subject						х		х		Х	X	
Staff + subject					Х	x	X	Х	х	х	X	
Staff + subject	X									х		
Staff + subject										х		
Staff + subject											X	
Staff + subject	X **					X **		X **				
	* Data from Eval	11 of the RE	STFUL Study	will be us	ed, since b	oth Evals typic	cally occu	r on the same	day			
	Staff + subject Subject Subject Staff Staff Staff Staff Staff + subject Staff + subject Investigator + subject Staff + subject	In-person	Day 0 Wks 1-24 In-person	Day 0	Day 0 Wks 1-24 Wks 25-32 Wk-2	Day 0	Day 0	Day 0	Day 0	Day 0 Wks 1-24 Wks 25-32 Wk-2 Wk-4 Wk-8 Wk-12 Wk-16 Wk-20 In-person or In-pe	Day 0 Wks 1-24 Wks 25-32 Wk-2 Wk-4 Wks-4 Wks-12 Wk-16 Wk-20 Wk-24	Day 0

		Eval 1	Eval 2	Eval 3	Eval 4	

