3.2 Method of Assigning Subjects to Treatment

All subjects who are enrolled in Arm 1 will be assigned to:

- NTX100 programmed to ACTIVE mode for Weeks 1-24
- No treatment for Weeks 25-32

and will be instructed to maintain constant dosage and schedule of RLS medication (if applicable) for Week 1-32.

All subjects who are enrolled in Arm 2 will be assigned to:

• No treatment for Weeks 1-24 and will be permitted to change RLS medication during the study.

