6.2 Stable Medication Population

The Stable Medication (SM) Population will include all eligible subjects who pass screening, are enrolled into the study, and do not report any of the following changes to prescription RLS medication between completion of the RESTFUL Study and Week 24 of CT-05:

- 1. New prescription RLS medication.
- 2. Change in dose of prescription RLS medication.
- 3. New prescription sleep medication.
- 4. Change in dose of prescription sleep medication.

The Stable Medication Population will be used for a secondary analysis of key secondary efficacy endpoints #6-11. This is intended to account for the differences in instructions regarding changes to prescription medications for Arms 1 and 2.

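### Per Protocol exclusions in SAP 6.3 have no Week-24 cut-off, so events in Arm 1's off-device Weeks 25-32 can remove valid Week-24 results from the secondary PP analyses

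*SAP*

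**What the plan says.** SAP 6.3 admits to the PP set subjects in Arms 1 and 2 who pass screening, undergo the assigned treatment and "have complete and evaluable Week 24 data, except that" a list of exclusions then applies. Three of the five exclusions matter here:

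- Rule 1: "Discontinuation from the study", with no time limit and no element of judgement.
- Rule 3: "Arm 1 only] Change to RLS medication during the study that is deemed clinically significant by the investigator".
- Rule 5: any other deviation that the investigator considers clinically significant, again with no time limit.

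For Arm 1, the study does not end at Week 24. SAP 3.1 says the arm "involves a 24-wk extension period of NTX100 device use followed by an 8-wk period without device use". SAP 3.2 assigns "No treatment for Weeks 25-32" and asks subjects to keep RLS medication constant for all 32 weeks. Protocol 16.12 still collects medication changes at Evaluation 9 (Week 32), and Protocol 16.15 states: "Study exit will occur at the conclusion of Eval #9". Arm 2 is complete 24 weeks after RESTFUL (Protocol 16.2).

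The primary and all key secondary endpoints (SAP 4.1 and 4.2) are Week-24 values. The neighbouring Stable Medication population (SAP 6.2) does carry a cut-off: it counts changes "between completion of the RESTFUL Study and Week 24 of CT-05". The protocol's own PP list (17.2.3) is as open-ended as the SAP's. Its medication rule is "Clinically significant change in dose or schedule of medication that affects RLS symptoms", with no time limit, so it supplies no cut-off to fall back on.

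**The concern.** Membership of an analysis set for a Week-24 endpoint should not depend on what happens after Week 24. Here it does, and only in Arm 1. Protocol 16.1 gives the purpose of the off-device period as observing RLS after treatment stops, so a dropout or medication change in that period may be a consequence of losing the device. The affected subjects could be those who benefited and relapsed, or those who never did well. The direction of any bias therefore cannot be stated in advance.

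The PP analyses are secondary, but they have a role. The ITT analysis relies on last observation carried forward (SAP 5.3), and the Stable Medication set is used only for key secondary endpoints 6 to 11. For the primary endpoint and key secondary endpoints 1 to 5, PP is the only alternative population planned (Tables 2.2 and 2.4). Table 2.6 compares the arms, and there the longer exclusion window applies to one side only.

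**Working it through.** The plan states no sample size (SAP 3.4), dropout rate or medication-change rate, so it has no figure to reproduce. The main check sets the rules against the timeline.

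**Step 1. Exclusion window by arm.** Arm 1: 24 weeks on device + 8 weeks off = 32 weeks. Arm 2: at most 24 weeks. Ratio 32/24 = 1.33. All endpoints sit at Week 24, so the last 8 weeks in Arm 1 can affect set membership but not the outcome.

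**Step 2. Which rules can act after Week 24.**

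| PP rule | Can it act in Weeks 25-32? | Judgement needed? |
|---|---|---|
| 1 Discontinuation | Yes | No |
| 2 Missing endpoint data | No, tied to the endpoint | n/a |
| 3 RLS medication change (Arm 1) | Yes | Yes, clinically significant |
| 4 Zero device uses (Arm 1) | No, settled by Week 24 | n/a |
| 5 Other deviation | Yes | Yes, clinically significant |

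**Step 3. What rule 1 adds.** A subject who leaves before Week 24 normally has no evaluable Week-24 data, and so already fails the entry condition and rule 2. Rule 1 therefore acts mainly on Arm 1 subjects who leave after a valid Week-24 assessment. Protocol 16.16 also allows removal in Arms 1 and 3 for a significant dose change of medication affecting sleep or RLS, with no time limit. Such a removal would trigger rule 1.

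**Step 4. Illustration of size (all counts assumed).** Take 40 Arm 1 subjects with evaluable Week-24 data and 28 responders: 28/40 = 70.0%. Let k be excluded for events in Weeks 25-32. The lower bound, if all k are responders, is (28 − k)/(40 − k). The upper bound, if none are, is 28/(40 − k).

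| k | Lower bound | Upper bound |
|---|---|---|
| 2 | 26/38 = 68.4% | 28/38 = 73.7% |
| 4 | 24/36 = 66.7% | 28/36 = 77.8% |
| 6 | 22/34 = 64.7% | 28/34 = 82.4% |

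No Week-24 outcome changes in any row.

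**Step 5. How large k might be.** Let d be the assumed share excluded by Week 24. Under a constant hazard, the further share excluded in Weeks 25-32 is 1 − (1 − d)^(8/24). For d = 5%, 10% and 20% this gives 1.7%, 3.5% and 7.2%, or about 0.7, 1.4 and 2.9 of 40 subjects. Six of 40 (15%) in 8 weeks would correspond to 1 − 0.85³ = 38.6% by Week 24 at the same hazard. The hazard could rise when the device is withdrawn, but the documents give no figure for that.

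**The case against.** The strongest reply is that no primary conclusion depends on PP. SAP 6.1 makes ITT the primary population for all efficacy endpoints, and the sequence in SAP 8.2 advances on the primary analyses. ITT keeps every Week-24 result. That stands, and it limits the point to Tables 2.2, 2.4 and 2.6.

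A second reply is that an analyst could apply the list as of Week 24, since entry is anchored to Week-24 data and rule 2 to the endpoint. The cut-off in SAP 6.2 does not settle this: it may show the intended window, or it may show that the authors write a limit where they want one. The Stable Medication set also has a different purpose. This reply stands only in part. The literal wording of rule 3 covers the whole study, and Step 3 shows that rule 1 adds little except after Week 24. In an open-label study the choice should not be left until the data are in hand.

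A reader might also infer more than the documents support:

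- That any medication change in Weeks 25-32 removes the subject. Rules 3 and 5 require the investigator to deem the event clinically significant, and removal under Protocol 16.16 is discretionary. Only rule 1 is automatic.
- That the PP result is worthless as a check on ITT. Losing a few subjects weakens a sensitivity analysis but does not void it. Both sets are tabulated, and Listing 1.1 shows population membership.
- That a shift spanning 18 points is to be expected. That is the distance between two extremes at k = 6, an assumed count above the 1 to 3 that the constant-hazard scenarios suggest.
- That a cut-off would make the arms symmetric. Rule 3 is Arm 1-only because Arm 2 may change medication; that difference remains.

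**Conclusion.** SAP 6.3 is wrong as written. Rules 1, 3 and 5 run to the end of the study, which in Arm 1 is 8 weeks after the endpoint. They can remove valid Week-24 results for later events, automatically under rule 1 and on investigator judgement under rules 3 and 5. The consequence is conditioning on post-endpoint events in one arm, bias of unknown direction, and some loss of precision, all confined to the secondary PP analyses.

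The size cannot be computed from the documents. With the assumed 40 subjects and a 70.0% responder rate, two late exclusions bound the shift at −1.6 to +3.7 percentage points and six at −5.3 to +12.4. These are extremes, not predictions. The finding itself rests on the wording and the timeline, not on these numbers.

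**What to change.** In SAP 6.3, limit rules 1, 3 and 5 to events up to and including the Week-24 assessment (Eval 8 in Arm 1, Eval 4 in Arm 2), consistent with the cut-off in SAP 6.2. Record the change in SAP 3.5. Rules 2 and 4 need no change. Nor do the planned Week-32 summaries, which are ITT tables.

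The cost is one phrase. No new data are needed, and Week-24 results that would otherwise be discarded are kept. If the PP set has already been built, state which reading was applied and how many Arm 1 subjects were excluded only for events after Week 24.

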6.3 Safety Analysis Population

The Safety Analysis Population will include all subjects enrolled. All analyses of adverse events will be based on this population.

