16.5. Screening

Potential subjects will be screened for eligibility based on the criteria in Section 7 above. A potential subject who signs the study consent and is eligible will be assigned the same study ID number assigned to them during the RESTFUL Study, will be considered enrolled, and will count towards the study's sample size.

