17.3. Safety

17.3.1. Safety Endpoints

The safety endpoint will be a descriptive analysis of adverse events (AEs) for both study arms, classified and tabulated by seriousness, relationship to the device, and severity.

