17.3.2. Safety Analysis

Frequency charts of adverse events occurring at any time during the study will be produced. The proportion of subjects in Arms 1 and 3 reporting one or more adverse events between study entry and Week 24 will be pooled and tabulated. Similar analyses will be done for SAEs and device-related SAEs. Safety analysis will include all subjects who were treated. A Statistical Analysis Plan (SAP) will be developed prior to completion of the first subject in Arm 1 or 3, which may include additional plans for safety analysis.

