8.3 Safety Analyses

The proportion of subjects having one or more adverse events (AEs) between study entry and Week 24 will be presented by Arm. The proportion of subjects reporting AEs between Week 25 and Week 32 will be presented for Arm 1. Similar analyses will be done for serious adverse events (SAEs), device-related SAEs, and device-related AEs

Adverse events will be coded using the Medical Dictionary for Regulatory Activities (MedDRA). AEs will be summarized at the subject level using counts and percentages by MedDRA system organ class (SOC) and preferred term (PT). AEs will also be summarized at the event level using

counts and percentages by SOC/PT and seriousness, by SOC/PT and severity, and by SOC/PT and relationship to the device.

Frequency charts of adverse events occurring at any time during the study will be produced. The proportion of subjects with at least one AE will be presented overall and by SOC. The proportion of subjects with at least one occurrence of individual AEs will be presented for AEs occurring in >3% of subjects overall or within either Arm.

This document, when printed, is valid only until its new revision gets released, or when it becomes obsolete in the eQMS. The user of a printed copy of this document is responsible for using the current revision and for discarding superseded or obsolete revisions. The most current version of this document always resides in the eQMS.

Noctrix Health, Inc. CONFIDENTIAL CL-7 v2.0

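### The SAP bases safety on all enrolled subjects and the protocol on treated subjects; the change is unrecorded, and several adverse-event summaries are not stated to be by Arm

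*SAP*

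**What the plan says.** **SAP.** The Safety Analysis Population section (the second of two numbered 6.3) reads "The Safety Analysis Population will include all subjects enrolled", and then "All analyses of adverse events will be based on this population". Enrolment does not depend on device use: under protocol 16.5, a subject who consents and is eligible "will be considered enrolled". SAP 3.1 adds: "Subjects enrolled in Arm 2 will receive no treatment with the NTX100 device during Arm 2".

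**Protocol.** Section 17.3.2 states "Safety analysis will include all subjects who were treated". The only pooled figure it plans is "The proportion of subjects in Arms 1 and 3 reporting one or more adverse events", and both of those arms use the device. Section 17.3.1 describes the endpoint as a "descriptive analysis of adverse events (AEs) for both study arms".

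**How the set is used.** SAP 8.3 has three parts.

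- The first gives proportions with AEs to Week 24 by Arm and extends this to SAEs, device-related SAEs and device-related AEs.
- The second plans subject-level summaries by system organ class (SOC) and preferred term (PT), and event-level summaries by seriousness, severity and relationship to the device. It names no arm.
- The third plans frequency charts, an any-AE proportion given overall and by SOC, and a display rule "for AEs occurring in >3% of subjects overall or within either Arm".

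**Change log.** SAP 3.5 itemises the simplified Per Protocol definition and the new Stable Medication population. It does not mention the safety set; only a general sentence about further modifications could cover it.

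**The concern.** A device adverse-event rate should be read per subject exposed to the device, which is what the protocol's treated-subjects rule provides. The SAP replaces that rule without saying so and admits two groups with no device exposure in CT-05: all of Arm 2, and any Arm 1 subject who never switches the device on. The second group is contemplated by the plan, since zero device use is a Per Protocol exclusion in both documents, but the SAP removes such subjects only from that population.

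Wherever a summary is not split by Arm, the reader would see a mixture of device and no-device subjects, followed for different lengths of time, in a table that looks like the device's safety profile.

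**Working it through.** Neither document gives arm sizes, an expected AE rate or a zero-use share, so there is no planned figure to reproduce. The sizes below rest on labelled assumptions.

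**1. Figures stated to be by Arm.** Let p be the device-related AE rate in treated Arm 1 subjects and z the share of enrolled Arm 1 subjects with zero use, taken to have no device-related AEs. The Arm 1 rate on the enrolled denominator is p × (1 − z). With p = 20% (assumed):

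| z (assumed) | Arm 1 rate shown |
|---|---|
| 0% | 20.0% |
| 2% | 0.20 × 0.98 = 19.6% |
| 5% | 0.20 × 0.95 = 19.0% |
| 10% | 0.20 × 0.90 = 18.0% |

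Arm 2 has its own denominator here, so its contribution to dilution is zero.

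**2. Figures not stated to be by Arm.** Let k be the ratio of Arm 2 to Arm 1 subjects, and p1 and p2 the two arms' rates. A pooled proportion is (p1 + k × p2)/(1 + k). It lies between the two arm rates and is lowest when p2 = 0, where it equals p1/(1 + k). With p1 = 20% (assumed):

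| k (assumed) | Lowest pooled value |
|---|---|
| 0.25 | 0.20/1.25 = 16.0% |
| 0.5 | 0.20/1.5 = 13.3% |
| 1.0 | 0.20/2.0 = 10.0% |

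These are bounds, not predictions. For AEs of any cause, p2 will not be zero.

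**3. Unequal observation.** Protocol Table 4 schedules AE monitoring in Arm 1 at Evals 2 to 8 up to Week 24, which is seven contacts. The Arm 2 schedule has it at Evals 2 to 4, at most three. Under protocol Table 5, a subject enrolled 16 weeks after RESTFUL has only Evals 3 and 4 after Eval 1, and one enrolled at 24 weeks has only Eval 4. That leaves two contacts and one contact respectively. Pooling can therefore lower even an any-AE proportion, for reasons unrelated to the device.

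**4. Event-level tables.** Tables 4.3 to 4.5 count events, so the subject-denominator formulas do not apply. If Table 4.5 is not split by Arm, however, Arm 2 events enter the total from which percentages by relationship to the device are taken, and the device-related share falls.

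**5. Display threshold.** A pooled rate is a weighted average of the two arm rates, so it cannot exceed 3% unless at least one arm does. Because the rule also admits an AE on either Arm's rate alone, pooling can neither hide an Arm 1 event nor add one. Zero-use subjects move the effective cut-off among treated Arm 1 subjects only to 0.03/0.98 = 3.06% for z = 2% and 0.03/0.90 = 3.33% for z = 10%.

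**The case against.** A reader might infer that Arm 2 sits in the denominator of the device-related AE rate, so that with, say, 45 and 30 subjects (assumed) a 20% rate would appear as 0.20 × 45/75 = 12%. The documents do not support that. SAP 8.3 puts the device-related proportions by Arm and specifies no pooled device-related rate.

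Other points on the plan's side also stand:

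- Reporting Arm 2 events is not itself a departure. Protocol Section 10 records AEs in all subjects from enrolment, Arm 2 has scheduled AE monitoring, and 17.3.1 speaks of both arms.
- The wording on overall and by SOC may mean all organ classes together rather than both Arms together.
- The table shells may already split Tables 4.1–4.5 by Arm. They were not in the material available, so absence from the prose does not prove absence from the plan.
- Zero use is probably rare. Arm 1 enrols RESTFUL completers re-screened for proper device operation (exclusion criterion 26), and a precautionary Per Protocol exclusion does not show that such subjects are expected.
- Arm 2 subjects are untreated only within CT-05; protocol 16.1 says all had 4 or 8 weeks of device use in RESTFUL.

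None of this removes the conflict between treated and enrolled. Support for showing Arm 2 events is not support for merging them with Arm 1, and the text of SAP 8.3 does not rule that out.

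**Conclusion.** Wrong as written, minor severity. The SAP's safety set contradicts protocol 17.3.2, and SAP 3.5 does not record the change. For the proportions stated to be by Arm, the only effect comes from zero-use Arm 1 subjects: a relative reduction equal to z, or 20% to 19% at an assumed 5%. For the SOC/PT summaries, the event-level summaries and the overall any-AE proportion, the text permits a mixture of device and no-device subjects with unequal follow-up. How far that would move a figure depends on arm sizes and Arm 2 event rates that the documents do not give, and on table layouts that could not be checked. It would be a stronger conclusion that the plan makes the device look safer on its device-related rates; the by-Arm wording of SAP 8.3 does not support it.

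**What to change.** In the SAP:

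- Define the device safety set as Arm 1 subjects with at least one CT-05 device use.
- Keep Arm 2 AEs as a separate no-device column, with its own denominator.
- State that Tables 4.1–4.5 and the frequency charts are by Arm.
- Drop any figure that pools Arms 1 and 2, or label it clearly as such.
- Keep Listing 4 on all enrolled subjects, so that an event in a zero-use Arm 1 subject is still reported.
- List the change to the safety set in Section 3.5.

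The 3% display rule can stay as it is. The cost is wording only: no new data are needed, and zero use must already be identified for the Per Protocol population. The downside is that displayed AE percentages may be slightly higher.
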